3.2.1.1. Inclusion criteria for patient survey

Patients will be required to meet all the following inclusion criteria:

1. Use of TROBALT: current use or at least one prescription filled within the previous three months.
2. 18 years of age or older.
3. Willing to take the online survey or have the survey administered via a telephone interview.

3.2.1.2. Exclusion criteria for patient survey:

Patients meeting any of the following criteria will not be eligible to take the survey:

1. Unable to understand and complete the survey by internet or phone.
2. Currently an employee of GSK [REDACTED]

3.2.1.3. Methods of Recruitment

Patients will be recruited by prescribers, who will be asked to provide survey invitations to their patients being treated with TROBALT. If the patient response rate using this recruitment method is lower than expected, then other options will be identified including patient panels, where available and approved by the country-specific Ethics Committee.

3.2.2. Neurologists prescribing anti-epileptic drugs

This survey aims to recruit a random sample of 300 neurologists prescribing AEDs and who have been sent the TROBALT Physician's Guide. A sample of 200 neurologists will be recruited from across the following countries (United Kingdom, Sweden, Denmark, Switzerland, Spain, Slovakia and Norway), and up to 100 neurologists will be recruited from Germany. If required, additional EU countries may be included in the survey to reach the minimum recruitment target. The recruitment will be from among those who have prescribed an anti-epileptic drug (AED) at least once in the last 3 months, and who were on the list to which a letter including the Physician's Guide TROBALT was distributed. The survey will aim to recruit at least 75 physicians (from the seven specified countries) and 50 physicians from Germany with experience of prescribing TROBALT for sub-analyses, as these individuals would be expected to be more aware of the risks of TROBALT. The sub-group of neurologists commonly referred to as 'epileptologists' are known from past experience to be the specialists who first initiate prescriptions of a new AED and were therefore specifically targeted for promotional activity by GSK and are the primary target of this survey.

As with the patient population, these numbers reflect a trade-off between what is practical in terms of recruitment, given the relatively low predicted prescribing of TROBALT, and providing sufficient precision around outcome estimates (proportion giving correct responses per question), and also to allow analysis of the sub-sample of neurologists who have prescribed TROBALT.

3.2.2.1. Inclusion criteria for physician survey

Physicians will be required to meet all the following inclusion criteria:

1. Must have prescribed an AED at least once in the last 3 months
2. Must be on the list to which the Physician's Guide for TROBALT was distributed.

3.2.2.2. Exclusion criteria for physician survey

Physicians meeting any of the following criteria will not be eligible to take the survey:

1. Currently an employee of GSK or [REDACTED]

3.2.2.3. Methods of Recruitment

The neurologists will be recruited through an invitation to participate in the survey. The invitation will direct the neurologist to the survey website to complete the survey. Invitations will be sent by e-mail to those neurologists for whom an e-mail address is available. For those neurologists without e-mail addresses, invitations will be sent by mail. If there is no response after the first invitation, then a second reminder invitation will be sent within 2 weeks after the first mailing.

Physicians will be paid the equivalent of €75 for their participation, which is fair market value for a survey estimated to take 20 minutes to complete.

3.3. Survey Design

The final study design is based on experience from risk management studies previously completed by GSK and [REDACTED] has designed and conducted assessment surveys in over 20 European countries to evaluate prescribers' understanding of risk messages. Recruitment and analytic strategies included in this proposal are similar to those programs. Further, both [REDACTED] and GSK have conducted similar knowledge, attitude and behavior surveys in the US to evaluate Risk Evaluation and Mitigation Strategies (REMS).

3.3.1. Questionnaire Structure

Each survey will be composed of multiple choice and close-ended questions. There will be no open-ended questions included. For statements or questions that use "true" or "yes" vs. "false" or "no" response options, the desired response for key risk messages is generally "true" or "yes" indicating knowledge of, or behavior in accordance with, the objectives of the program. However, some questions are formatted to have the respondent disagree with the statement as written by providing response options of "false" or "no" to avoid having the same affirmative answer for all desired responses.

Both physicians and patients will be provided a unique code in the survey invitation letter and will be asked to provide the unique code to gain access to the online survey or when calling the Survey Coordinating Center. The code will be deactivated after use to minimize the possibility for fraud.

3.3.2. Measures to minimise bias in the surveys

The following are measures to minimise bias in the surveys:

- Telephone interviewers are highly trained and use a standardized script to administer interviews.
- All questions will be programmed to ensure that questions are asked in the appropriate sequence. Skip patterns will be clearly indicated. Respondents cannot go back to a question once the question has been answered and cannot skip ahead. All questions must be answered in order to complete the survey.
- Response options presented in a list will be randomized to minimize positional bias.
- Programming will be reviewed by quality control and simulated users (User Acceptance Testing) prior to implementing the survey.

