- 1) 250 patients recruited from across the following countries (United Kingdom, Sweden, Denmark, Switzerland, Spain, Slovakia and Norway) and up to 100 patients from Germany who are currently using or have filled a prescription for TROBALT at least once in the last 3 months.
- 2) 200 neurologists who have prescribed an anti-epileptic drug (AED) at least once in the last 3 months, and who were on the list to which a letter containing the Physician's Guide for TROBALT was distributed from across the following countries (United Kingdom, Sweden, Denmark, Switzerland, Spain, Slovakia and Norway). At least 75 of the neurologists will have prescribed TROBALT. The survey will also aim to include up to 100 neurologists from Germany of which approximately 50 will have prescribed TROBALT.

Patients eligible for the survey will be asked to take the survey online or via a telephone interview if the latter is preferred. Neurologists will be invited to take the survey online.

The selected countries were the first five countries to launch TROBALT (Germany, Denmark, United Kingdom, Switzerland and Sweden) and an additional three countries with launch in 2011, but with relatively high rates of uptake of TROBALT (Spain, Slovakia and Norway). The selection of countries includes Switzerland, which is not part of the European Union. However, the key messages regarding the risks with TROBALT are in alignment. The rationale for surveying the first five countries to launch is so that any issues identified from these countries regarding the effectiveness of the Physician's Guide and PIL in communicating the risks of TROBALT can be addressed as soon as possible, and the key messages can be revised in a timely manner. In addition, these countries are likely to provide the greatest number of neurologists with experience of prescribing TROBALT, and their patients.

Study Endpoints/Assessments

The primary outcome of the survey is the proportion of patients/neurologists providing correct responses to a series of questions concerning the significant risks associated with TROBALT. The risks evaluated will be those described in the TROBALT PIL and in the Physician's Guide.

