Neurologist told me			
Family doctor or general practitioner (GP) told me			
Online			
Patient Information Leaflet			
Patient Support Group			

16. The Patient Information Leaflet says TROBALT can cause heart problems. Which one of the following heart conditions can TROBALT cause? (Select one answer)

- Chest pain
- **Making my heart beat too fast or too slow**
- Heart attack
- All of the above
- None of the above

17. Which of the following raises the chance for effects on heart rhythm when you take TROBALT? Please answer “yes,” “no” or “I don’t know” for each one.

	Yes	No	I Don’t Know
Taking other medicines	X	O	O
Smoking	O	X	O
Already having a heart problem	X	O	O
Having asthma	O	X	O
Being 65 years old or older	X	O	O

18. In what country do you live? (Will have drop-down menu of all countries in the survey).

19. What is your gender?

- Male
- Female

20. What is the highest level of education you have completed?

- Some secondary school (EU equivalent) or less
- Finished secondary school
- Some university or technical/trade school
- Graduated university
- Post graduate studies
- Prefer not to answer

[CLOSING] Thank you for completing the survey. The following are the correct answers to the survey questions about TROBALT.

The following are the correct answers to the survey questions about TROBALT.

Which side effects are more likely to happen with TROBALT?

- Cannot pass urine (urinary retention)
- Being confused
- Seeing or hearing things that are not there (hallucinations)
- Severe mental problems, such as being out of touch with reality (psychotic disorders)

You should call your doctor right away if you have which symptoms?

- Trouble starting to pass urine (urinary retention)
- Thoughts of harming or killing yourself (suicidality)

The Patient Information Leaflet says TROBALT can cause heart problems. Which heart condition can TROBALT cause?

- Making my heart beat too fast or too slow

Which factors raise the chance for effects on heart rhythm when you take TROBALT?

- Taking other medicines
- Already having a heart problem
- Being 65 years old or older

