The information in this survey and the Patient Information Leaflet (PIL) should not take the place of talking with your health care professional. If you have any questions about your condition or treatment, or if you would like more information about TROBALT, talk to your health care professional. The Patient Information Leaflet can be obtained from the following website: <http://www.gsk.com/products/prescription-medicines/trobalt.htm>.

Thank You

Appendix 5 Questionnaire for Neurologists who Prescribe AEDs and were Sent the TROBALT Letter Containing the Physician's GuideScreening Questions:

1. Do you agree to take part in this survey?
 - **Yes**
 - No (Exclude)

2. When was the last time you prescribed an anti-epileptic drug for a patient?
 - **Less than a month ago**
 - Between 1 and 2 months ago
 - Between 2 and 3 months ago
 - More than 3 months ago (Exclude)

3. Have you ever prescribed TROBALT?
 - **Yes**
 - No
 - I don't know

4. In which country is your primary medical practice?
 - **Germany**
 - Denmark
 - United Kingdom
 - Switzerland
 - Sweden
 - Spain
 - Slovakia
 - Norway
 - Other (exclude)

[QUOTAS WILL BE ESTABLISHED FOR 200 NEUROLOGISTS FROM UK, SWEDEN, DENMARK, SWITZERLAND, SPAIN, SLOVAKIA, AND NORWAY; AT LEAST 75 SHOULD HAVE PRESCRIBED TORBALT. QUOTA OF 100 NEUROLOGISTS FROM GERMANY, OF WHICH AT LEAST 50 SHOULD HAVE PRESCRIBED TROBALT.]

5. Are you an employee of GlaxoSmithKline or [REDACTED] Corporation?
 - **Yes (Exclude)**
 - **No**

Questionnaire for Neurologists who Prescribe AEDs and Were Sent the TROBALT Letter Containing the Physician's Guide

[CORRECT ANSWERS ARE INDICATED IN BOLD]

6. For which of the following conditions is TROBALT approved for use?
- Migraine
 - **Partial-onset seizures**
 - All types of seizures
 - All of the above
 - None of the above
 - I don't know
7. Is TROBALT indicated for use as monotherapy?
- Yes
 - **No**
 - I don't know
8. What is the maximum recommended daily maintenance dose of TROBALT for most patients? (Please select the best response.)
- 600 mg
 - 900 mg
 - **1200 mg**
 - 2000 mg
 - None of the above
 - I don't know
9. Which one of the following statements is true? (Please select the best response.)
- TROBALT should be taken once a day.
 - TROBALT should be taken twice a day.
 - **TROBALT should be taken three times a day.**
 - TROBALT should be taken four times a day.
 - None of the above
 - I don't know

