10. When increasing the dose, what is the maximum total daily dose at which TROBALT can be increased once every 7 days? (Please select the best response.)
- 50 mg
 - **150 mg**
 - 300 mg
 - 600 mg
 - None of the above
11. Which one of the following statements is true? (Please select the best response.)
- There are no lower age limits for TROBALT usage.
 - The youngest age at which TROBALT can be used is 12.
 - **The youngest age at which TROBALT can be used is 18.**
 - I don't know

Please respond “true,” “false” or “I don’t know” to each of the following questions:

12. The quickest time by which the minimum maintenance dose of 600mg should be reached is the third week?
- **True**
 - False
 - I don’t know
13. For the general population, the recommended total initial dosage should be 150mg per day for one week.
- True
 - **False**
 - I don’t know
14. People taking TROBALT had a higher chance of experiencing which of the following risks in clinical studies? (Please select all that apply)
- **Urinary retention**
 - **Confusional state**
 - **Hallucinations**
 - **Psychotic disorders**
 - Myocardial infarction
 - Renal carcinoma
 - All of the above
 - None of the above
 - I don’t know
15. It is known from controlled studies that adverse events related to voiding dysfunction generally tend to be reported how soon after starting TROBALT?
- Within the first week
 - **Within the first 8 weeks**
 - After 4 months
 - After 12 months
 - I don’t know
16. It is known from controlled studies that confusional state, hallucinations, and/or psychotic disorders generally tend to be reported how soon after starting TROBALT?
- 4 weeks
 - **8 weeks**
 - 12 weeks
 - 16 weeks
 - I don’t know

17. Which of the following urinary symptoms, if any, should you specifically advise patients taking TROBALT to watch out for? (Please select the best response.)
- Pain when urinating
 - Difficulty starting urination
 - Slow stream
 - Inability to pass urine
 - **All of the above**
 - None of the above
 - I don't know
18. According to the TROBALT Physician's Guide, appropriate dose titration may minimize the risk of which of the following adverse events? (Please select the best response.)
- QT prolongation
 - **CNS side effects such as hallucinations**
 - Urinary retention
 - All of the above
 - None of the above
 - I don't know

[DO NOT DISPLAY QUESTIONS 19 and 20 FOR RESPONDENTS FROM SWITZERLAND]

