19. Using the Treatment Initiation Pack, by which week can the patient reach a dose of 600mg/day?
- 2 weeks
 - **3 weeks**
 - 4 weeks
 - 5 weeks
 - None of the above
20. At what dose has TROBALT been shown to produce a possible QT prolonging effect?
- 600 mg
 - 900 mg
 - **1200mg**
 - 1800 mg
 - I don't know
21. For which patients is it recommended that an ECG is recorded before initiating TROBALT? (Please select all that apply.)
- Patients with hypertension
 - **Patients with congestive heart failure**
 - **Patients with ventricular hypertrophy**

- **Patients with hypokalemia**
 - All of the above
 - None of the above
 - I don't know
22. What should you do in a patient with a QTc of **more** than 440ms before starting TROBALT? (Please select the best response)
- Recheck the ECG 1 week after the first dose
 - Recheck the ECG at monthly intervals
 - **Recheck the ECG after reaching the maintenance dose**
 - I don't know
23. Which new cardiac effects in particular should you warn your patients about after prescribing TROBALT? (Please select all that apply)
- Syncope
 - Palpitations
 - Any other symptoms of arrhythmia
 - **All of above**
 - None of the above
24. How would you classify your primary medical specialty?
- Neurology
 - Neurosurgery
 - Epileptology
 - Other (specify) _____ [FREE TEXT]
 -
25. Have you read the TROBALT information letter that was sent at the launch of TROBALT?
- Yes
 - No
 - I don't know
26. From which of the following sources have you learned about the risks associated with use of TROBALT? (Please select all that apply)
- TROBALT launch letter
 - GlaxoSmithKline medical information
 - Other health care professionals
 - GlaxoSmithKline promotional materials
 - GlaxoSmithKline sales representatives
 - Journal article
 - GlaxoSmithKline-sponsored educational meeting
 - None of the above

27. What is your gender?

- Male
- Female

28. For how many years have you been in medical practice?

- Less than 3 years
- 3-5 years
- 6-10 years
- 11-15 years
- 16-20 years
- More than 20 years
- Prefer not to answer

29. Do you agree to provide your name and address so that we can issue a payment for your time in completing this survey?

- Yes (Record name and address)
- No

Name _____

Address _____

[CLOSING] That ends the survey. Thank you again for your help. The correct answers to the questions about TROBALT follow.

The following are the correct answers to the survey questions about TROBALT.

For which condition is TROBALT approved for use?

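### Section 3.3.2 randomises listed response options with no stated exception, which conflicts with the All/None of the above options in the questionnaires, two of which are the keyed answer

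*Protocol*

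**What the plan says.** The ordering rule stands in Protocol section 3.3.2, among the measures against bias: "Response options presented in a list will be randomized to minimize positional bias". The same list adds that "Respondents cannot go back to a question once the question has been answered and cannot skip ahead", and that "Programming will be reviewed by quality control and simulated users (User Acceptance Testing) prior to implementing the survey".

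The neurologist survey is run on screen (Protocol Summary, Study Design: "Neurologists will be invited to take the survey online"). The patient questionnaire is used both on screen and by telephone.

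Appendix 5 marks its key by the note "CORRECT ANSWERS ARE INDICATED IN BOLD". Two items are keyed to the *All* option:

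- Question 17, "Which of the following urinary symptoms, if any, should you specifically advise patients taking TROBALT to watch out for", lists four symptoms, then *All of the above*, *None of the above* and *I don't know*. It asks for the single best response.
- Question 23, "Which new cardiac effects in particular should you warn your patients about after prescribing TROBALT", lists three effects, then *All of above* and *None of the above*. It allows several answers.

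The closing answer sheet in Appendix 5 repeats both keys. In Appendix 3, patient question 16, "Which one of the following heart conditions can TROBALT cause", also offers *All* and *None*, but is keyed to a substantive answer.

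Sections 4.3, 4.4, 6.2.1 and 6.2.2 define the primary outcome as the proportion answering correctly, item by item.

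**The concern.** An option that refers to what is above it has a fixed meaning only if its place in the list is fixed. Section 3.3.2 removes that condition, while the answer key in Appendix 5 relies on it. A neurologist who knows that every listed symptom matters may see the *All* option in the middle or at the top of the list. Read literally, it then leaves out something true.

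The outcome is reported per item, so no composite score dilutes a flawed item. Questions 17 and 23 ask what neurologists should tell patients about urinary and cardiac symptoms, and both topics are headings in the Physician's Guide letter (Appendix 1). A display artefact there could be read as poor knowledge, in a study meant to judge whether the educational plan works. A respondent who notices the oddity later cannot return to the item.

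**Working it through.** The protocol gives no figure on this point, so there is none to reproduce.

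**Extent.** The neurologist knowledge items are questions 6 to 23, which is 18 items. Those with an *All* and/or *None of the above* option are questions 6, 8, 9, 10, 14, 17, 18, 19, 21 and 23: ten of 18. Patient question 16 adds one.

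**Is there an exception elsewhere?** The questionnaires do carry programming notes: skips in Appendix 3, and quotas and the Switzerland display rule in Appendix 5. None pins an option or protects a scale.

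**How often is the keyed label incomplete?** Assume every order of the options is equally likely. With k true options, *All* is equally likely to hold any of the k + 1 places among those options and itself. So P(all k lie above it) = 1/(k + 1). The positions of *None* and *I don't know* do not enter.

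- Question 17, k = 4: 1/5 complete, so 1 − 1/5 = 80% of displays have at least one symptom below the key. Enumerating all 7! = 5040 orders gives the same.
- Question 23, k = 3: 1/4 complete, so 1 − 1/4 = 75%. Enumerating all 5! = 120 orders gives the same.

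**How often does the label stop being the best response in question 17?** The number of symptoms above *All* is 0, 1, 2, 3 or 4, each with probability 1/5. With two or more above, the label read literally still covers more than any single symptom does: 3/5 = 60% of displays. With one or none above it no longer does: 2/5 = 40%.

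**Effect on the proportion correct.** For a keyed item, loss = d × L × K, where d is the share of displays that mislead a literal reader, L the share of knowledgeable respondents who read the label literally, and K the true proportion who know the answer. For question 17, d is 0.80 if any incompleteness misleads and 0.40 if the best-response wording is followed. For question 23, d is at most 0.75. The protocol gives neither L nor K. If nobody reads literally, L = 0 and the loss is zero. The direction is downward; the amount is not identified.

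**Does the remedy work?** With *All*, *None* and *I don't know* fixed at the end and only the symptoms or effects shuffled, the key covers every true option in 100% of displays of both items. Fixing only *None* and *I don't know* leaves 80% and 75% unchanged.

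**The case against.** The strongest reply is that the sentence is a one-line summary whose purpose is to limit positional bias. Which options are anchored is often settled in a programming specification, and an *All* option at the top of a list is the kind of thing that simulated-user testing catches. This is fair as far as it goes: the protocol is silent on exceptions and does not expressly rule them out, so the percentages describe a build that follows the sentence as written. But testing checks a build against its stated rule, and the only stated rule is to randomise.

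The other objections limit the size of the effect, and they stand:

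- Many respondents will read the label as meaning all of these.
- In question 17 the label remains the best response in 60% of displays.
- In question 23 a literal reader can tick the effects one by one. The protocol does not say how that is scored, and the analysis plan may settle it. If such answers count as correct, the loss can vanish.

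Three stronger readings are tempting, and the protocol does not support them:

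- A reader might infer a loss large enough to exceed the margins of error in Table 1. That needs an assumed share of literal readers, which has no basis in the document.
- A reader might infer that *None of the above*, shown above the key, becomes a true answer that is scored wrong. In question 17 it is literally true only if no symptom lies above it, which is 1/5 of orders. In items such as 8 and 9, a respondent who knows the answer sees it on screen and is asked for the best response.
- A reader might infer that shuffled recency lists in the screeners will wrongly exclude people. Each option there is a self-contained label, and nothing in the document shows that errors would follow.

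**Conclusion.** The sentence in section 3.3.2 is wrong as written. It conflicts with ten of the 18 neurologist knowledge items and patient question 16, most clearly with the keys of neurologist questions 17 and 23. If it is built literally with a uniform shuffle, the keyed label has at least one true option below it in 80% (question 17) and 75% (question 23) of displays. In question 17 it is no longer the best literal response in 40%.

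The bias in the per-item proportion correct is downward and cannot be sized from the protocol. Shuffled ordered lists (dose, time, age, years, recency) are harder to read, but the correct answer stays the same. This should be corrected before programming. It does not show that the survey results would be materially distorted.

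**What to change.** Replace the sentence in section 3.3.2 with: *Unordered substantive options will be randomised; All of the above, None of the above, Other and I don't know stay fixed at the end; ordered scales keep their natural order.* Apply the same rule in the programming specification and in the telephone script, where an *All* option heard mid-list is harder still to interpret. User acceptance testing can then check the build against it.

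The cost is one sentence and a programming flag per item. Question content and answer key stay as they are, and substantive options are still shuffled, so the protection against positional bias remains.
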